7.1.3. Severity of an Adverse Event

The severity of each adverse event must be recorded as one of the following:

- Mild:** No limitation of usual activities
- Moderate:** Some limitation of usual activities
- Severe:** Inability to carry out usual activities

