7.1.6. Protocol-Defined Adverse Events of Special Interest

For purposes of this protocol, the following are considered protocol-defined adverse events of special interest to be sent to the sponsor's GPSP Department for evaluation:

- ophthalmic-related adverse events of at least moderate severity, as determined by the investigator
- severe hypersensitivity reactions or anaphylaxis (see [Appendix C](#))

Hypersensitivity reactions will be monitored using the diagnostic criteria for anaphylaxis as outlined by the 2006 Joint National Institute of Allergy and Infectious Disease/Food Allergy and Anaphylaxis Network Second Symposium on Anaphylaxis ([Sampson et al 2006](#)). The clinical criteria for diagnosing anaphylaxis are provided in [Appendix C](#). In the event of suspected anaphylaxis, vital signs (including oxygen saturation and respiration rate) will be measured.

The process for reporting a protocol-defined adverse event of special interest will be the same as that for reporting a serious adverse event (Section [7.1.5.3](#)). Protocol-defined adverse events of

special interest to be reported to GPSP can either be serious or nonserious, according to the criteria outlined in Section 7.1.5.1.

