
 severe hypersensitivity reactions or anaphylaxis (see Appendix C) 	
 severe hypersensitivity reactions or anaphylaxis (see Appendix C) 	Updated to include anaphylactic reactions
Section 15 References		

 
Lindgren KN, Mastren VL, Tiburzi MJ, Ford DP, Bleecker ML. The factor structure of the Profile of Mood States (POMS) and its relationship to occupational lead exposure. J
	
National Institutes of Health. NIH Clinical Center Patient Education Materials Giving a Subcutaneous Injection. Bethesda, MD: National Institutes of Health Clinical Center; 2016.
	
Two references were deleted because they were no longer cited in the document and 1 reference was added

Original text with changes shown	New wording	Reason/justification for change

Occup Environ Med 1999;41(1):3-10. National Institutes of Health. NIH Clinical Center Patient Education Materials Giving a Subcutaneous Injection. Bethesda, MD: National Institutes of Health Clinical Center; 2016.
		

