This Statistical Analysis Plan (SAP) describes the planned analysis and reporting for Teva Branded Pharmaceutical Products R&D, Inc. study TV48125-PN-20028, (A Multicenter, Randomized, Double-Blind, Placebo-Controlled, Proof of Concept Study of the Efficacy and Safety of Fremanezumab for Treatment of Patients with Fibromyalgia), and was written in accordance with SOP GBP_RD_702 (Statistical Analysis Plan).

The reader of this SAP is encouraged to read the study protocol for details on the conduct of this study, the operational aspects of clinical assessments, and the timing for completing the participation of a patient in this study.

The SAP is intended to be in agreement with the protocol, especially with regards to the primary and all secondary endpoints and their respective analyses. However, the SAP may contain more details regarding these particular points of interest, or other types of analyses (e.g. other endpoints). When differences exist in descriptions or explanations provided in the study protocol and this SAP, the SAP prevails; the differences will be explained in the Clinical Study Report (CSR).

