
A secondary objective of the study is to evaluate the safety and tolerability of fremanezumab administered subcutaneously in adult patients with FM.
	
The safety and tolerability endpoints are as follows:
 
 • occurrence of adverse events • change from randomization to week 12 in the clinical laboratory tests (serum chemistry, hematology, and urinalysis) • change from baseline to week 12 in vital signs (pulse, respiratory rate, systolic and diastolic blood pressure, and oral body temperature measurements at each visit) • clinically significant changes in physical examination, including body weight • abnormal standard 12-lead electrocardiogram (ECG) findings • tolerability at the injection site including but not limited to pain, erythema, induration, and ecchymosis • occurrence of hypersensitivity/anaphylaxis reactions using standardized criteria (Appendix C of the study protocol) • suicidal ideation and behavior as measured by the Columbia-Suicide Severity Rating Scale (C-SSRS) • number (%) of patients who did not complete the treatment (Kaplan-Meier Survival Analysis) due to adverse events

1.2. [REDACTED]
[REDACTED]

		
 • [REDACTED] • [REDACTED]
		
 • [REDACTED] • [REDACTED] • [REDACTED] • [REDACTED] • [REDACTED] • [REDACTED] • [REDACTED]

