8.3. Adverse Events

An adverse event (AE) is any untoward medical occurrence in a patient administered a pharmaceutical product which does not necessarily have to have a causal relationship with this treatment.

For recording of AE, the study period is defined for each patient as the time period from signature of the informed consent form (ICF) to the end of the follow-up period or the early termination visit for patients who discontinued from the study for any reason. Any AE occurring on or after the first dose of study drug is considered a treatment-emergent AE (TEAE). All AE summaries will be conducted for TEAEs.

The following are considered protocol-defined adverse events of special interest (AESI) to be sent to the sponsor's Global Patient Safety and Pharmacovigilance (GPSP) Department for evaluation:

- ophthalmic-related adverse events of at least moderate severity, as determined by the investigator
- severe hypersensitivity reactions

All AEs will be coded using MedDRA. The incidence of AEs will be summarized using descriptive statistics by SOC and preferred term (PT). Each patient will be counted only once in each PT or SOC category for the analyses of safety.

Statistical Analysis Plan

Summaries will be presented for all AEs (overall and by severity), AEs determined by the investigator to be related to test IMP (ie, reasonable possibility) (defined as related or with missing relationship) (overall, overall by severity, serious AEs, and AESI), serious AEs, AESI, AEs causing discontinuation from treatment, AEs causing early termination from the study, injection site AEs, and AEs leading to death.

Listings of AEs, AESI, serious AEs, injection site AEs, and AEs leading to early termination will be presented separately.

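### The SAP's list of adverse events of special interest omits anaphylaxis, which the current protocol includes, and no planned table counts patients with the stated hypersensitivity/anaphylaxis endpoint

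*SAP*

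**What the plan says.** - **Protocol 7.1.6** names two AESIs. The first is ophthalmic events of at least moderate severity. The second is "severe hypersensitivity reactions or anaphylaxis", with a reference to Appendix C. The Amendment 04 entry in protocol Section 16.3 gives the reason for adding anaphylaxis: "Updated to include anaphylactic reactions".
- **SAP 8.3** introduces its list as the protocol-defined one. The ophthalmic item matches. The second item reads only "severe hypersensitivity reactions", without anaphylaxis or Appendix C.
- **SAP 1.1** lists as a safety endpoint "occurrence of hypersensitivity/anaphylaxis reactions using standardized criteria (Appendix C of the study protocol"). It sets no severity threshold.
- **Protocol 7.1.3** grades severity by how far the event limits usual activities; moderate means "Some limitation of usual activities".
- **Protocol Appendix C** defines anaphylaxis by combinations of signs and exposure and uses no severity grade.
- **SAP Introduction**: where the two documents differ, "the SAP prevails", and the differences are to be explained in the clinical study report. **SAP Section 18**, on changes from the protocol, is marked as not applicable.

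**The concern.** There are two linked gaps.

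First, the SAP carries a definition that the sponsor had already widened. The SAP refers to Amendment 05 (in 6.2.4 and 8.5.2), so it was written after Amendment 04 brought anaphylaxis in. It nevertheless presents the narrower wording as the protocol's and declares no change. A programmer who builds the AESI flag from SAP 8.3 would select on severity and not on Appendix C.

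Second, an endpoint named in SAP 1.1 has no analysis of its own in the safety and tolerability sections.

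Hypersensitivity matters more here than a routine event category. Protocol 1.3.1 treats severe hypersensitivity as a potential risk of the drug and notes postmarketing reports that include anaphylaxis. It also says that mild and moderate hypersensitivity occurred at similar incidence on drug and placebo in the migraine programme. That is a grouped comparison, and this SAP plans none. For a rare event, the AESI table is where a reader will look first.

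**Working it through.** The plan gives no figure to reproduce on this point, so the check is a comparison of texts followed by tracing one event through the planned outputs.

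**Step 1: can the two definitions part?** Take a patient with acute generalised hives and wheeze after an injection. Appendix C criterion a requires acute skin or mucosal involvement plus respiratory compromise or a blood pressure fall, so the event qualifies as anaphylaxis. If the investigator judges that usual activities were only partly limited, 7.1.3 makes it moderate. Under protocol 7.1.6 it is an AESI, through the anaphylaxis limb. Under SAP 8.3, with severity read as the 7.1.3 grade, it is not. Protocol 7.8 also treats the two limbs as separate triggers, calling for an anti-drug antibody sample on either a severe hypersensitivity reaction or anaphylaxis.

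**Step 2: where does that event appear in SAP 8.3?**

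| Planned output | Captured on the SAP wording? |
|---|---|
| AESI summary | No |
| Related-AESI summary | No (yes on the protocol wording, if judged related) |
| AESI listing | No |
| All treatment-emergent events by system organ class and preferred term, overall and by severity | Yes, under its coded term(s) |
| Related, serious, discontinuation and early-termination summaries | Yes, if it meets the condition |
| Listing of all adverse events | Yes |
| Per-arm count of patients meeting Appendix C | Not planned |

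SAP 8.1 presents safety summaries by treatment received, so the captured rows are split by arm.

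**Step 3: can the SAP 1.1 endpoint be read from the captured rows?** Protocol 7.1.2 has signs recorded individually unless they are considered manifestations of a condition. Without a unifying diagnosis, hives and wheeze sit under separate preferred terms. With one, hypersensitivity is still spread over several terms. Adding rows does not give a patient count, because one patient can appear in several. No part of SAP Section 8 groups hypersensitivity terms or applies Appendix C, and Section 9 covers injection-site findings only. The per-arm number of patients with the endpoint therefore cannot be derived from the planned tables.

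**Step 4: scale.** At the planned 80 per arm, one patient is 1/80 = 1.25%. SAP 2.5.1 and 2.5.2 say the trial ended early for futility, and final arm sizes are not stated. The amendment history gives 153 randomized at Amendment 05. Assuming an equal split, that is 153/3 = 51 per arm, and 1/51 = 1.96%. With arms assumed between 51 and 80, one case is 1.25% to 1.96% of an arm. This shows what one patient weighs; it does not estimate how often the wording would matter.

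**The case against.** The strongest reply is that little is lost. SAP 8.3 tabulates every treatment-emergent event by arm, preferred term and severity, and lists them all. An anaphylaxis would often also be serious: protocol 7.1.5.1 gives intensive treatment of allergic bronchospasm as an example of an important medical event. Protocol 4.3 adds that hypersensitivity may lead to discontinuation of the drug, and such events have their own summary. All of this stands. A reader might infer that a moderate-graded anaphylaxis would go unreported, or that mild and moderate hypersensitivity would never be compared between arms. The documents do not support either inference. What is missing is the AESI flag and the grouped patient count.

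A second reply is that severe hypersensitivity already includes anaphylaxis. One sentence in protocol 1.3.1 uses the terms that way, and 7.1.6 says hypersensitivity will be monitored with the anaphylaxis criteria. The reading is possible. However, other sentences in 1.3.1, and 7.1.6 and 7.8, name the two as alternatives, and Amendment 04 would have had nothing to add if one contained the other. The SAP wording is at best ambiguous.

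A third reply is that sites report AESIs under protocol 7.1.6, which the SAP cannot alter. If the AESI table is built from site-reported AESIs, the event stays in. The SAP does not say whether it uses site reports or applies its own list, so the omission is possible and not established.

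Finally, the SAP promises that differences from the protocol will be explained in the study report. That helps only if the difference is noticed, and Section 18 records none.

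**Conclusion.** The concern holds in limited form. SAP 8.3 does not reproduce the AESI definition it attributes to the protocol. As worded, it can drop a moderate-graded Appendix C anaphylaxis from the AESI summary, the related-AESI summary and the AESI listing. The SAP 1.1 hypersensitivity/anaphylaxis endpoint has no dedicated analysis, and no planned table gives the number (%) of patients per arm, whether for hypersensitivity of any severity or for events meeting Appendix C.

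A reader might go further and conclude that the trial cannot address this endpoint at all. That is too strong. The events are collected, coded, tabulated by arm and listed, and severe reactions reach the AESI table, so the gap is one of grouping and counting.

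The first part assumes that severity in SAP 8.3 means the 7.1.3 grade and that the AESI table follows the SAP list. The second part needs neither assumption. It rests on the SAP text supplied: the immunogenicity analysis is deferred to a separate SAP (Section 14) and SAP 6.4, under efficacy, is redacted, but nothing says that either covers this endpoint.

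**What to change.** 1. In SAP 8.3, restore the protocol 7.1.6 wording for the second AESI, including anaphylaxis and the reference to Appendix C. If the narrower list was intended, record the change and its reason in Section 18.
2. Add one descriptive by-arm table, with a listing, of the number (%) of patients with (a) any hypersensitivity reaction, using a term list fixed before unblinding, and (b) anaphylaxis by Appendix C, both regardless of severity grade.

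The cost is a line of text, one table with its listing, agreement on a term list, and a small blinded review of recorded adverse events against Appendix C before database lock. That review would be new: the checks already scheduled in SAP 3.4 and 5.7 concern the per-protocol set and protocol deviations. SAP 2.5.2 already provides for amendments approved before lock. No new data collection is needed.

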8.4. Deaths

If any patient dies during the study all relevant information will be discussed in the patient’s narratives included in CSR.

8.5. Clinical Laboratory Tests

Clinical laboratory tests (serum chemistry, hematology, coagulation, and urinalysis) will be performed at the time points detailed in Table 1 in the study protocol using a central laboratory. Clinical laboratory tests will be performed using a central laboratory. Specific laboratory tests to be performed are provided in [Table 3](#).

Table 3: Clinical Laboratory Tests

Serum Chemistry	Hematology and Coagulation	Urinalysis
Calcium	Hemoglobin	Protein
Phosphate	Hematocrit	Glucose
Sodium	Erythrocytes	Ketones
Potassium	Platelets	Hemoglobin
Chloride	Leukocytes	pH
Creatinine	
 • Neutrophils • Lymphocytes • Eosinophils • Monocytes • Basophils 	Specific gravity
Glucose	Lymphocytes atypical	Microscopic tests
Blood urea nitrogen (BUN)	Prothrombin International	
 • Bacteria • Erythrocytes • Leucocytes • Crystals • Casts
Urate	Normalized Ratio (INR)	
Alanine aminotransferase (ALT)		
Aspartate aminotransferase (AST)		
Lactate dehydrogenase (LDH)		
Gamma-glutamyl transpeptidase (GGT)		
Alkaline phosphatase		
Bicarbonate		
Carbon dioxide		
Protein		
Albumin		
Bilirubin		
Direct bilirubin		
Hepatitis B		

Laboratory test results will be presented in standard international (SI) units.

Statistical Analysis Plan

Summary statistics for chemistry, hematology, coagulation, and urinalysis laboratory tests will be presented at baseline, week 4, week 8, week 12, week 16, and last assessment. Laboratory values and changes from baseline to week 4, week 8, week 12, week 16, and last assessment will be summarized using descriptive statistics.

Shifts (below, within, and above the normal range) from baseline to week 4, week 8, week 12, week 16, and last assessment will be summarized using patient counts.

Summaries of potentially clinically significant abnormal values will include all postbaseline values (including scheduled, unscheduled, and withdrawal visits). The incidence of potentially clinically significant abnormal values will be summarized for laboratory variables using descriptive statistics with the criteria specified in [Table 4](#).

Table 4: Criteria for Potentially Clinically Significant Laboratory Values

Test	Criterion value
Serum chemistry	
Alanine aminotransferase (ALT)	$\geq 3x$ ULN
Aspartate aminotransferase (AST)	$\geq 3x$ ULN
Alkaline phosphatase (ALP)	$\geq 3x$ ULN
Gamma-glutamyl transpeptidase (GGT)	$\geq 3x$ ULN
Lactate dehydrogenase (LDH)	$\geq 3x$ ULN
Blood urea nitrogen (BUN)	≥ 10.71 mmol/L
Creatinine	≥ 177 μ mol/L
Uric acid	Men ≥ 625 μ mol/L
	Women ≥ 506 μ mol/L
Bilirubin (total)	≥ 34.2 μ mol/L
Hematology	
Hematocrit	Men < 0.37 L/L
	Women < 0.32 L/L
Hemoglobin	Men ≤ 115 g/L
	Women ≤ 95 g/L
White blood cell (WBC) counts	$\leq 3 \times 10^9/L$ $\geq 20 \times 10^9/L$
Eosinophils	$\geq 10\%$
Absolute neutrophil counts (ANC)	$\leq 1 \times 10^9/L$
Platelet counts	$\leq 75 \times 10^9/L$ $\geq 700 \times 10^9/L$
Urinalysis	
Blood (HGB)	≥ 2 unit increase from baseline
Glucose	≥ 2 unit increase from baseline

Test	Criterion value
Ketones	≥2 unit increase from baseline
Total protein	≥2 unit increase from baseline

ULN=upper limit of normal range.

Listings for potentially clinically significant abnormal laboratory data will be presented.

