4. GENERAL ISSUES FOR DATA ANALYSIS

4.1. General

Descriptive statistics for continuous variables include n, mean, SD, standard error (SE), median, minimum, and maximum. In addition, for fremanezumab concentration, percentage coefficient of variation (%CV) and geometric mean will also be calculated. Descriptive statistics for categorical variables include patient counts and percentages, missing category will be displayed as appropriate.

Summaries of potentially clinically significant abnormal values will include all postbaseline values (including scheduled, unscheduled, and early termination visits).

For by-visit analyses, if there are multiple assessments at a scheduled postbaseline visit then the last non-missing scheduled assessment at that visit will be used for the summary. If a visit has scheduled and unscheduled assessments, the scheduled assessment will be used for the analysis. If a visit only has unscheduled assessments, the unscheduled assessments will be used for analyses; if there are more than one unscheduled visits, the assessment from the last unscheduled visit will be used for analyses.

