4.2. Specification of Baseline Values

The baseline values are defined as the last non-missing assessments before the first dose of IMP unless otherwise specified.

Baseline value for the average of the daily average PI-NRS pain score is defined as the average of the daily average PI-NRS score over the last 14 days before the first dose of IMP drug (day -14 to day -1) and will be calculated using formula [1].

Baseline value for the average of the daily worst PI-NRS pain score is defined as the average of the daily worst PI-NRS score over the last 14 days before the first dose of IMP (day -14 to day -1) and will be calculated using formula [1].

The baseline values for the following variables are measured on the day of the first study drug (day 1) before the first dose of study drug.

- individual components of the FIQR: symptom subscore, impact subscore, and functional subscore score
- PROMIS Physical Function SF12a score
- PROMIS Fatigue SF8a score
- HADS score
- EQ-5D-5L
- POMS-2A Short Form score

The baseline value for IMD assessment rating is measured at the screening visit.

PROMIS Sleep Disturbance SF 8a score are collected on e-diary weekly during BAPS. The baseline PROMIS Sleep Disturbance SF 8a scores will be the mean of the weekly scores recorded during last 14 days before the first dose of IMP drug (day -14 to day -1).

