8.7. Vital Signs

Vital signs (blood pressure [systolic/diastolic], respiratory rate, oral body temperature, and pulse) will be measured at the time points detailed in Table 1 in the study protocol.

Summary statistics for vital signs (blood pressure [systolic/diastolic], respiratory rate, oral body temperature, and pulse) will be presented at baseline, week 4, week 8, week 12, week 16 (end of treatment), week 30 (end of study), and last assessment. Vital signs values and changes from baseline to each visit will be summarized using descriptive statistics.

Summaries of potentially clinically significant abnormal values will include all postbaseline values (including scheduled, unscheduled, and withdrawal visits). The incidence of potentially clinically significant abnormal values will be summarized using descriptive statistics with the criteria specified in Table 5. Systolic and diastolic blood pressure will be included in all summaries.

Table 5 specifies the criteria for identifying vital signs as potentially clinically significant abnormal values. Note that in order to qualify as potentially clinically significant abnormal, a value needs to meet both criteria below: ie, have a value beyond the criterion value and a change of at least the magnitude specified in the change relative to baseline column.

Table 5: Criteria for Potentially Clinically Significant Vital Signs

Vital Sign	Criterion value	Change relative to baseline
Pulse	≥120 bpm	Increase of ≥15
	≤50 bpm	Decrease of ≥15
Systolic blood pressure	≥180 mm Hg	Increase of ≥20
	≤90 mm Hg	Decrease of ≥20
Diastolic blood pressure	≥105 mm Hg	Increase of ≥15
	≤50 mm Hg	Decrease of ≥15
Respiratory rate	<10 breaths/min	
Body temperature	≥38.3°C	Change of ≥1.1°C

bpm=beats per minute

Listings for potentially clinically significant abnormal laboratory data will be presented.

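### The counts of potentially clinically significant chemistry and hematology values in SAP 8.5 do not separate patients who already met the Table 4 cutoff at baseline

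*SAP*

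**What the plan says.** SAP 8.5 defines the input to the laboratory summary: "Summaries of potentially clinically significant abnormal values will include all postbaseline values (including scheduled, unscheduled, and withdrawal visits"). It then defines the measure: "The incidence of potentially clinically significant abnormal values will be summarized for laboratory variables using descriptive statistics with the criteria specified in" Table 4. SAP 4.1 gives the same general rule: "Summaries of potentially clinically significant abnormal values will include all postbaseline values (including scheduled, unscheduled, and early termination visits"). Neither section sets a condition on baseline status, an at-risk denominator or a rule for new onset.

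Table 4, "Criteria for Potentially Clinically Significant Laboratory Values", has 19 tests:

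- Nine serum chemistry and six hematology tests, each with an absolute cutoff, such as GGT at or above 3 times ULN, eosinophils at or above 10%, or a low hematocrit by sex.
- Four urinalysis tests (blood, glucose, ketones, total protein), each needing a 2-"unit increase from baseline" or more.

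For vital signs, SAP 8.7 applies Table 5 with this condition: "a value needs to meet both criteria below: ie, have a value beyond the criterion value and a change of at least the magnitude specified". Respiratory rate is the only vital sign there with no change listed.

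SAP 4.2 defines the reference point: "The baseline values are defined as the last non-missing assessments before the first dose of IMP unless otherwise specified". Baseline status on each cutoff can therefore be derived from data already collected. Protocol 9.8.2 speaks of comparing values with predefined criteria and does not address baseline status.

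**The concern.** The word *incidence*, applied to postbaseline values only, invites a reader to take the percentage as abnormalities that appeared after dosing. For the 15 absolute-cutoff tests the stated rule does not deliver that. A patient whose eosinophils were at 10% or more before the first dose and stayed there is counted in the same cell as a patient who crossed the cutoff on study.

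There are two consequences. Each arm's percentage is higher than its new-onset percentage. In addition, baseline carriers are spread over the arms by chance, so with a few cases per arm they can create or mask an apparent difference. This is a safety table read by eye, with no model to adjust for baseline.

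**Working it through.** The plan states no figure for this point, so there is none to reproduce. The check has a textual part and an illustration on assumed rates.

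**Textual part.** Of the 19 tests in Table 4, 9 + 6 = 15 (79%) allow a patient who was beyond the cutoff at baseline, and still is, to be counted. The other 4 (21%) do not, because an unchanged abnormality shows no rise. In Table 5, four of the five vital signs need a change as well as a cutoff.

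**Illustration.** Let *b* be the share meeting a given cutoff at baseline, *r* the share of those who still meet it afterwards, and *q* the new-onset rate among the rest. Only the planned 80 patients per arm comes from the documents (SAP 2.4); *b*, *r* and *q* are assumptions.

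- Reported rate = *b·r* + (1 − *b*)·*q*
- New cases = (1 − *b*)·*q*
- Pre-existing share of the reported count = *b·r* / [*b·r* + (1 − *b*)·*q*]

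Worked case, *b* = 3%, *r* = 80%, *q* = 1%: 0.024 + 0.0097 = 0.0337. That is 80 × 0.0337 = 2.7 patients per arm, of whom 80 × 0.0097 = 0.78 are new. The pre-existing share is 0.024 / 0.0337 = 71%.

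Other cases with *r* = 80%:

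| *b* | *q* | *b·r* | (1 − *b*)·*q* | Reported per 80 | New per 80 | Pre-existing share |
|---|---|---|---|---|---|---|
| 0.25% | 2% | 0.0020 | 0.01995 | 1.8 | 1.6 | 9% |
| 0.5% | 2% | 0.0040 | 0.0199 | 1.9 | 1.6 | 17% |
| 1% | 2% | 0.0080 | 0.0198 | 2.2 | 1.6 | 29% |
| 3% | 2% | 0.0240 | 0.0194 | 3.5 | 1.6 | 55% |
| 5% | 2% | 0.0400 | 0.0190 | 4.7 | 1.5 | 68% |
| 5% | 1% | 0.0400 | 0.0095 | 4.0 | 0.8 | 81% |

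Varying *r* from 50% to 100% at *q* = 2% moves the share to 20–34% for *b* = 1% and 57–73% for *b* = 5%. The share does not depend on the number of patients.

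**Chance imbalance.** Treat the number of baseline carriers in each of two arms as independent binomials with 80 patients. The probability that the arms differ by three or more carriers is 24% at *b* = 3% and 36% at *b* = 5%. The trial was stopped for futility (SAP 2.5), so the arms may be smaller. With 50 per arm the probabilities are 13% and 24%, but three patients are then 6 percentage points (3/50) instead of 3.75 (3/80).

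**The case against.** The strongest points on the other side are these.

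- **The SAP is open about its rule.** It says all postbaseline values are used and never calls these counts treatment-emergent; that term is defined only for adverse events (SAP 8.3). A reader might infer that the plan presents pre-existing abnormalities as treatment-emergent findings. The text does not say so. What stands is that the two kinds of patient are not separated.
- **Entry criteria remove some baseline cases.** Protocol 4.2 excludes clinically significant or unstable hematologic, renal, hepatic and other disease at the investigator's discretion, informed by the laboratory panels (f). It also excludes clinically significant ALT or AST elevations (t), and creatinine above 1.5 times ULN or evidence of renal disease (v). This makes low prevalences plausible for several tests and is why the bottom of the range matters. Criterion f is discretionary, and no numeric limit covers GGT, LDH, BUN, uric acid, eosinophils, WBC, hematocrit, hemoglobin or platelets.
- **Baseline context is reported elsewhere.** SAP 8.5 plans changes from baseline, shift tables and listings of flagged values. Results judged clinically significant become adverse events (Protocol 7.4). These help, but the shifts use the normal range. A patient mildly above normal at baseline and one already beyond the Table 4 cutoff fall in the same category.
- **Dropping baseline-positive patients could hide a signal,** such as a GGT that was at the cutoff and then rose sharply. This is right, and the remedy has to keep them visible.

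Two further inferences are not supported. One is that the whole laboratory table is affected: the urinalysis rows are already relative to baseline. The other is that one arm is favoured: allocation is randomised 1:1:1, so baseline carriers are balanced on average.

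**Conclusion.** The point holds for the 15 serum chemistry and hematology tests. As written, SAP 8.5 counts persistent pre-existing abnormalities together with new ones, unlike its treatment of urinalysis and nearly all vital signs. The harm is limited to inflated counts and added noise in a descriptive safety table. No efficacy result and no planned inference depends on it.

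The size is unknown. A pre-existing share of 29% to 81% requires 1% to 5% of patients beyond a single cutoff at baseline, with 80% persistence and 1% to 2% new onset. If the entry criteria hold baseline prevalence to 0.25% to 0.5% and new onset is 2%, the share is 9% to 17%. A reader might take the upper figures as showing that most flagged patients are pre-existing; without baseline rates the documents cannot support that. This is a cheap improvement to make before the tables are produced, not an error that invalidates the summary.

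**What to change.** In SAP 8.5, keep the count over all postbaseline values and the listing of flagged values. Then add, for the chemistry and hematology tests:

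- Results by baseline status on the same Table 4 cutoff: not met, met, missing. For WBC and platelets, which have a low and a high cutoff, take baseline status separately for each.
- A new-onset percentage whose denominator is patients who did not meet the criterion at baseline and have at least one postbaseline value.
- A separate row for patients who met the criterion at baseline, with their postbaseline status and worst change from baseline, so that worsening stays visible.

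The urinalysis rows need no change. The cost is a few sentences in the SAP, an extra condition in the table program, a slightly longer table and denominators that differ by test. No new data are needed.
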